12.1.4 Definitions for Statistical Data Analysis

The following definitions (**Table 17**) for statistical analyses/presentations will be used:

Table 17: Definition of terms for the statistical analysis

Term	Definition
Baseline Value	The last valid assessment at the last available time point prior to first product use in the Exposure Period.

For 24-hour urine collections, the collection sample will be labelled by the day in which the collection started. As an example if the 24-hour urine sample is collected from Day 5 to Day 6, it will be analyzed and reported as the Day 5 sample.

12.1.5 Handling of Dropouts or Missing Data (including outside the limits of quantification)

For laboratory parameters:

- Values below the lower limit of quantification (LLOQ) will be imputed using LLOQ/2. For values above the upper limit of quantification (ULOQ), the ULOQ will be imputed.
- The number of values below LLOQ or above ULOQ will be presented in each summary table. If 50% or more data are below LLOQ or above ULOQ, only the number (%) of value below LLOQ or above ULOQ will be reported in the summaries, together with minimum and maximum of the observed values.
- Missing data at Baseline will not be imputed.

For daily product use data:

- If at least 75% of the daily product use assessments over a period are available, with no more than 7-days of consecutive missing data:
 - Product use categories will be defined based on percentage of THS 2.2 use calculated by averaging non missing consumption data over the analysis interval.
 - Compliance to randomized product will be defined based on the available product use data.
- If less than 75% of the daily product use assessments over a period are available, or product use data is missing over a period of more than 7 consecutive days:
 - Product use category and Compliance to randomized product will be considered missing.

For MNWS, QSU-brief, and mCEQ questionnaire data:

- Total scores and domain or subscale scores will be derived by averaging the individual non-missing item scores if at least 50% are non-missing, otherwise they will be set to missing.

For missing or partial dates:

- Missing dates for Day 30, 60, and Day 90 Visits will be imputed for the calculation of product use exposure within periods by adding 30, 60, or 90 days to the randomization date. If the imputed date falls after discharge date (e.g. for early terminated subjects), then the discharge date will be used.
- Missing or Partial dates will not be imputed for Adverse Events (AEs), for medical history, and for concomitant medications, but assumptions will be made as follows to assign them to specific analysis categories:

Date information (*)	AE Category	Disease Category	Medication Category
Missing date or Partial date, (e.g., --May2012, or ----2011) if month/year is the same as, or later than the month and/or year of Screening.	Product-emergent	Concomitant disease	Concomitant medication
Partial date, (e.g., --May2012, or ----2011). If month and/or year is earlier than the month and/or year of Screening.	Not product-emergent	Medical history	Prior medication

(*) Missing or partial date refers to stop date for disease and medication categories

AEs missing relatedness or severity:

AEs missing relatedness or severity assessment will be displayed in the AE tables as per the rule described for incidence and prevalence of AEs in 12.5.4.2.1 “All Adverse Events”.

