12.1.4 Handling of Missing Values and of Values outside the Detection Limits

Descriptive summaries will be provided for the evaluable data with no imputation.

Missing values for the endpoints analyzed via the mixed model method will not be directly imputed as they are handled within the analysis itself.

Values below the lower limit of quantification (LLOQ) will be imputed using $0.5 \times \text{LLOQ}$. For values above the upper limit of quantification (ULOQ), the ULOQ will be used for calculation and reporting in summary tables. The number of values below LLOQ or above ULOQ will be presented in each summary table. If 50% or more data are below LLOQ or above ULOQ, only the number (%) of value below LLOQ or above ULOQ will be reported in the summaries, together with minimum and maximum of the observed values.

For questionnaire data, total scores and domain or subscale scores may use a certain degree of imputation by averaging across individual item scores.

Further details will be provided in the SAP.

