12.1 General Considerations

Data analysis will be performed using SAS[®] Version 9.2 or higher.

Data listings will be provided for all data collected as required by this protocol, ordered by arm and subject and timepoint (if applicable), unless otherwise stated. Summary statistics and statistical analyses will only be presented for data where detailed in this SAP. All unscheduled assessments will be included in the listings.

The protocol specifies that the assumptions of the analysis of variance model will be tested. The distribution of the data will be visually checked for normality or log-normality by means of histograms. Markedly non-(log)normally distributed data will be transformed or analyzed by appropriate non-parametric methods. For all endpoints, the assumed distribution is mentioned in the SAP.

For log-transformed endpoints, the least squares (LS) means and estimate of the difference along with its 95% CI will be back-transformed before presenting in the tables. The geometric LS means for each arm along with the reduction (i.e: 100% - ratio of CHTP 1.2 : CC (%)) and 95% CI will be presented in the tables. For naturally distributed data, the obtained LS Means for each arm along with the difference between these and 95% CI will be presented in the tables.

For data summarized on the log scale (or data summarized in its natural scale and for which a log transform was applied in an attempt to get normality), markedly non-lognormally distributed parameters will be analyzed with bootstrapping the log-transformed data using the SAS PROC SURVEYSELECT procedure. The seed to be used in any analysis will be contained in the SAS output and will be different for each analysis.

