12.5.1.1 Primary endpoints

COHb in blood, and urinary concentrations adjusted for creatinine of MHBMA, 3-HPMA and S-PMA, and total NNAL will be summarized on the log-scale as detailed in **Section 12.1.3 “Descriptive Statistics”**. Distributions will be tested for log-normality and appropriate non-parametric methods will be used in case of non-lognormally distributed data as described in **12.1 General Considerations**.

The values and percent changes from baseline in the concentration adjusted for creatinine of MHBMA, 3-HPMA, S-PMA and total NNAL will be listed and summarized along with the COHb concentrations and percent changes from baseline (Tables 15.2.3.3-7.1, 15.2.3.3-7.2 and Listing 15.3.3.1). This will also be summarized by sex, by average cigarette consumption over the previous 6 weeks prior to admission and by product use category (Tables 15.2.3.3-7.1.1, 15.2.3.3-7.1.2 and 15.2.3.3-7.1.3).

The log-transformed data will be analyzed by means of an ANCOVA (on Day 5 for COHb, MHBMA, 3-HPMA and S-PMA and Day 90 Visit for total NNAL) using arm as covariate adjusting for sex and average cigarette consumption over the previous 6 weeks prior to admission, and log-transformed baseline value of endpoint.

The SAS code to be used for COHb in blood, and urinary concentrations adjusted for creatinine of MHBMA, 3-HPMA and S-PMA on Day 5 and total NNAL adjusted for creatinine at Day 90 Visit is shown below:

```
Proc mixed data=_data_ ;  
Class arm sex cigarette_cons ;  
Model log (Value) = log (baseline) sex cigarette_cons arm ;  
Lsmeans arm / pdiff =control('CC') alpha=0.05 cl ;  
Run ;
```

The least squares (LS) means and estimate of the difference along with its 95% CI will be back-transformed before presenting in the tables. The geometric LS means for each arm along with the reduction (i.e: 100% - ratio of CHTP 1.2 : CC (%)) and 95% CI will be presented in the tables (Table 15.2.3.1).

In addition line graphs will be produced for arm geometric means (and 95% CI) over all timepoints for COHb in blood, and urinary concentrations adjusted for creatinine of MHBMA, 3-HPMA, S-PMA and total NNAL (Figure 15.1.1.1-5).

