12.5.2.1.2 Urinary Biomarkers of Exposure

The Urinary Biomarkers of Exposure assessed as secondary endpoints are total 1-OHP, Total NNN, 4-ABP, 1-NA, 2-NA, o-tol, CEMA, HEMA, Total 3-OH-B[a]P, HMPMA assessed at Day 5 and Day 90 Visit, MHBMA, 3-HPMA and S-PMA assessed at Day 90 Visit and Total NNAL assessed at Day 5.

The urine parameters will be expressed as concentrations adjusted for creatinine. In addition, the quantity excreted over 24 hours for all Biomarkers of Exposure will be presented. These endpoints will be log-transformed.

The values and percent changes for urinary BoExp in the quantity excreted over 24-hours and the concentration adjusted for creatinine will be listed and summarized (Table 15.2.4.3-12.1 and 15.2.4.3-12.2 and Listing 15.3.3.1). In addition line graphs will be produced for arm geometric means (and 95% CI) over all timepoints (Figure 15.1.2.1-25).

The analysis will compare the log-transformed urinary concentrations adjusted for creatinine and the quantity excreted over 24-hours between the CHTP 1.2 and CC arms on Day 5 and Day 90 Visit for 1-OHP, total NNN, 4-ABP, 1-NA, 2-NA, o-tol, CEMA, HEMA, Total 3-OH-B[a]P, HMPMA.

The analysis will also compare the log-transformed urinary concentrations adjusted for creatinine and the quantity excreted over 24-hours between the CHTP 1.2 and CC arms for MHBMA, 3-HPMA, S-PMA at Day 90 Visit and for total NNAL at Day 5 as well as the quantity excreted over 24-hours between the arms for MHBMA, 3-HPMA and S-PMA at Day 5 and for total NNAL at Day 90 Visit.

The statistical model and SAS code will be the same as described in Section 12.5.1.1 “**Primary endpoints**”. Note that for the analyses at Day 90 Visit, the p-value will only be shown if the one-sided p-value at Day 5 was significant (i.e. < 0.025). The geometric LS means for each arm along with the reduction (i.e: 100% - ratio of CHTP 1.2 : CC (%)) and 95% CI will be presented in the tables (Table 15.2.3.2, Table 15.2.4.1)

The least squares (LS) means and estimate of the difference along with its 95% CI will be back-transformed before presenting in the tables. The geometric LS means for each arm along with the reduction (i.e: 100% - ratio of CHTP 1.2 : CC (%)) and 95% CI will be presented in the tables (Table 15.2.4.1).

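### LLOQ/2 substitution enters the biomarker ANCOVA without a cap, though the SAP withholds summary means at 50% BLOQ; with heavy BLOQ in the CHTP 1.2 arm the reported reduction and its CI can be wrong

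*SAP*

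**What the plan says.** SAP 12.1.5 (laboratory parameters): "Values below the lower limit of quantification (LLOQ) will be imputed using LLOQ/2". Protocol 12.1.4 has the same rule. Neither caps the share of values that may be replaced.

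The next bullet of SAP 12.1.5 reads: "If 50% or more data are below LLOQ or above ULOQ, only the number (%) of value below LLOQ". It goes on to allow only the minimum and maximum beside the count, and it is confined to the summaries. It does not say whether the 50% is counted by arm, by visit or over both arms.

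SAP 12.5.1.1: "The log-transformed data will be analyzed by means of an ANCOVA". The model line is "Model log (Value) = log (baseline) sex cigarette_cons arm", with no term for censoring. The output is back-transformed to geometric LS means, a % reduction and a 95% CI. SAP 12.5.2.1.2 reuses this model for the secondary urinary biomarkers and again reports "The geometric LS means for each arm along with the reduction".

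Two safeguards exist. The first is a distribution check: "Distributions will be tested for log-normality and appropriate non-parametric methods will be used in case of non-lognormally distributed data". SAP 12.1 specifies the fallback: "markedly non-lognormally distributed parameters will be analyzed with bootstrapping the log-transformed data". The second is that each summary table shows how many values lie outside the limits.

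**The concern.** The two rules in SAP 12.1.5 do not fit together. A descriptive geometric mean could be withheld because half the values are BLOQ, while a model-based one from the same substituted values is the headline result. No censored-data or sensitivity analysis for BLOQ values is planned.

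One-sided censoring is plausible. SAP Table 8 expects CHTP 1.2 levels at 15% of CC for MHBMA and 20% for S-PMA. If BLOQ values occur, most will be in the CHTP 1.2 arm, and substitution then moves one arm's log mean and not the other's.

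At stake are the size of the reduction and its interval. The study is designed around a reduction of 50% or more (SAP 5.4.2), but the formal test in SAP 12.5.1.2 carries no 50% margin. Any statement about 50% must therefore rest on the estimate and CI.

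**Working it through.** **Inputs.** Ratios and CVs come from SAP Tables 8 and 9: MHBMA 0.15 (0.70), S-PMA 0.20 (0.70), 3-HPMA 0.30 (0.50), COHb 0.40 (0.32), total NNAL 0.30 (0.60). Allocation is 80:40, with 40:40 for NNAL if half the CHTP 1.2 arm stays in the PP set (SAP section 8). The BLOQ share p in the CHTP 1.2 arm is an assumption and is varied.

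**The plan's own figures.** Log SD σ = √ln(1+CV²); effect = ln(MR/0.5).
- COHb: σ = 0.312; SE = 0.312 × √(1/80+1/40) = 0.0605; 0.223/0.0605 − 1.96 = 1.73, so power is 95.8% (plan: 96%).
- Total NNAL, 40:40: σ = 0.5545; SE = 0.124; 0.511/0.124 − 1.96 = 2.16, so power is 98.5% (plan: 98%).

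The log-normal set-up matches the plan.

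**Shift from LLOQ/2.** Take a fixed limit at the p-quantile of an arm, with c = Φ⁻¹(p). That arm's log mean moves by

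shift = p(σc − ln 2) + σφ(c).

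For CV 0.70, σ = √ln 1.49 = 0.6315:
- p = 0.50: 0.5(0 − 0.693) + 0.6315 × 0.399 = −0.095. Ratio 0.15 becomes 0.1365, so the reduction is overstated.
- p = 0.75: 0.75(0.426 − 0.693) + 0.6315 × 0.318 = 0.000. No net shift.
- p = 0.90: 0.9(0.809 − 0.693) + 0.6315 × 0.1755 = +0.215. The CC arm (about 4% BLOQ) moves by −0.019, so the ratio becomes 0.15 × e^0.234 = 0.1895 and the reduction is understated.

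**Simulation without covariates** (20,000 trials per setting): mean estimated reduction / 95% CI coverage.

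| BLOQ in CHTP 1.2 | MHBMA (true 85%) | S-PMA (true 80%) |
|---|---|---|
| 10% | 85.6% / 0.95 | 80.8% / 0.95 |
| 25% | 86.1% / 0.92 | 81.5% / 0.92 |
| 50% | 86.3% / 0.88 | 81.8% / 0.88 |
| 75% | 84.9% / 0.93 | 79.7% / 0.92 |
| 90% | 81.1% / 0.30 | 74.2% / 0.26 |

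**Simulation of the ANCOVA** (log baseline, assumed correlation 0.5; sex and consumption omitted). At true ratio 0.15 it gives 0.136 with 87% coverage at 50% BLOQ, and 0.190 with 24% at 90%. At true ratio 0.20, coverage at 90% is 20%.

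**Interval width.** At 20-50% BLOQ the model SE rises from 0.106 to 0.112-0.117, and the CHTP 1.2 log SD rises from 0.63 to 0.72 at 20% and 0.66 at 50%. The coverage loss there comes from the shift. The SE is clearly too small only from about 75%; by 90% the SD has fallen to 0.30.

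**Creatinine.** Four of the five primary endpoints are biomarker divided by creatinine (SAP 7.1.1), so the limit on the analysed scale is LLOQ/creatinine and differs by subject. With an assumed creatinine CV of 0.4, coverage is 92-93% at 40-50% BLOQ and 2-3% at 90%.

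**Smaller CVs.** At 50% BLOQ, total NNAL reads 73.3% and 3-HPMA 74.3% (both true 70%), and COHb reads 67.9% (true 60%). The documents do not show whether COHb would have any BLOQ values.

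**Test and 50% reading.** For ratio < 1, power stays about 100% under the planning effects and type I error is 2.4-2.9%. At a true ratio of 0.5, the chance that the CI lies wholly below 0.5 rises from 2.5% to about 6% at 25-50% BLOQ with CV 0.70. With COHb's CV it rises to 28% at 25% BLOQ and 72% at 50%.

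**Censored likelihood** (fixed limit, no covariates, 600 trials per setting). At 25-90% BLOQ the mean reductions are 84.9-85.1% for MHBMA, 79.9-80.2% for S-PMA, 59.8-60.0% for COHb and 69.9-71.9% for NNAL, with coverage 93.5-97%.

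**The case against.** The strongest reply is that nothing in the documents shows BLOQ values will be common. Protocol 4.3 asks for biomarkers that are readily detected with validated methods, and a low CHTP 1.2/CC ratio is not evidence of values below the limit. That stands: a reader might infer that the reported reductions will be artefacts of the LLOQ, and the documents do not support it. At moderate BLOQ shares the error for MHBMA and S-PMA is small.

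It also stands that the confirmatory conclusion is safe, since the test is of ratio < 1. A reader might further infer that substitution makes the CI too narrow throughout; at 20-50% BLOQ the SE goes up.

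The appeal to safeguards stands only in part. A histogram would expose a pile-up of imputed values, and the BLOQ counts would disclose it. But the specified fallback bootstraps values already substituted, so it carries the same bias. In a trial run at ratio 0.15 (500 trials), percentile-bootstrap coverage was 85% at 50% BLOQ and 36% at 90%.

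A fair warning about remedies: a low trigger for replacing the planned model, such as 10% BLOQ, is not justified, because coverage there is still 94-95%.

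**Conclusion.** The gap is real and its effect conditional. SAP 12.1.5 applies a BLOQ limit to descriptive means but none to the ANCOVA, and its fallback does not repair the estimate. For the two endpoints with the lowest expected ratios, the bias is minor up to about 60% BLOQ in the CHTP 1.2 arm. Its direction reverses near 75% with a fixed limit, and it is serious by 90%: the reduction is understated by 85 − 81.1 = 3.9 points for MHBMA and 80 − 74.2 = 5.8 points for S-PMA, and the CI rarely contains the true value.

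These figures rest on log-normal data with the plan's ratios and CVs and on assumed BLOQ shares, baseline correlation and creatinine CV. If BLOQ values prove rare, nothing changes. The confirmatory claim is not in doubt; the size of the reduction, its CI and any 50% statement are what need protection.

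**What to change.** Amend SAP 12.1.5, 12.5.1.1 and 12.5.2.1.2 before database lock:

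- State that the 50% rule is applied by arm and timepoint and covers the model tables. When either arm has 50% or more BLOQ, no LLOQ/2-based geometric LS mean or % reduction is the main estimate. A pooled count would be too lax: half of 120 is 60 subjects, or 60/80 = 75% of the CHTP 1.2 arm if all BLOQ values fall there.
- For any primary or secondary biomarker with BLOQ values, pre-specify a left-censored normal regression on the log scale with the same covariates (PROC LIFEREG or NLMIXED). Censor at LLOQ/creatinine for creatinine-adjusted endpoints, LLOQ × urine volume for quantity excreted, and LLOQ itself for COHb.
- Make it a sensitivity analysis below 50% BLOQ and the reported estimate at or above 50%. The switch then uses the SAP's own threshold.

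The cost is a paragraph of SAP text and a few lines of SAS. The downside is two estimates to report and explain wherever BLOQ values occur.

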12.1.5.1 Insufficient Data for Analysis/Presentation

If there are no values/events at the general value then the break out should not be presented. For example if the number of related AEs is zero then no presentation by severity of related events at the single level will be produced.

Some of the TFLs will have no subject for data for presentation. If this occurs, the blank TFL shell will be presented with a message printed in the center of the table, such as, “No serious adverse events occurred for this study.”

For categories of summaries that have <4 subjects, only the number of subjects and the minimum and maximum will be shown.

12.1.6 Handling of Unplanned Data

Unscheduled assessments will be excluded from the summary statistics. Unscheduled assessments will be labelled as unscheduled in the listings and mapped to the study day using the date of the study day until midnight.

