9.5 Early Termination Procedures

Early termination procedures will be as follows, unless the subject refuses to do so:

Table 19 Time Schedule - Early Termination Procedures

Time	Blood Sample	Procedures	Additional Information
Start of Procedure		Early Termination	
During the visit		AE/SAE recording	
During the visit		Concomitant medications	
During the visit	√	Clinical laboratory parameters (hematology, clinical chemistry)	After at least 10 hours of fasting
During the visit		Spirometry pre- and post-bronchodilator (recording of FEV ₁ , FVC, FEV ₁ /FVC)	Has to be done 1 hour of not smoking At rest in sitting position for at least 15 minutes prior to pulmonary function testing In sitting position

Confidentiality Statement

Data and information contained in this document are considered to constitute trade secrets and confidential commercial information, and the legal protections provided to such trade secrets and confidential information are hereby claimed under the provisions of applicable law. No part of this document may be publicly disclosed without the written consent of Philip Morris Products S.A.

Time	Blood Sample	Procedures	Additional Information
Start of Procedure		Early Termination	
			All post-bronchodilator spirometry testing will be performed 15 - 30 minutes post administration of salbutamol
During the visit		Vital signs (blood pressure, pulse rate, respiratory rate)	At least 5 minutes in supine position, at least 15 minutes after having stopped using IP
During the visit		ECG	At least 10 minutes in supine position prior to recording
During the visit		Physical examination, body weight, and calculated BMI	
During the visit		Safety urine analysis	
During the visit		Urine pregnancy test (females only)	
During the visit		Information on the risks of smoking, smoking cessation advice and debriefing.	
During the visit		Discharge from the site	

Abbreviations: AE = Adverse event; BMI = Body mass index; ECG = Electrocardiogram; FEV₁ = Forced expiratory volume in 1 second; FVC = Forced vital capacity; SAE = Serious adverse event

Confidentiality Statement

Data and information contained in this document are considered to constitute trade secrets and confidential commercial information, and the legal protections provided to such trade secrets and confidential information are hereby claimed under the provisions of applicable law. No part of this document may be publicly disclosed without the written consent of Philip Morris Products S.A.

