12.5.4 Safety Analysis

In general, all safety data will be listed and tabulated by product arm, using the approach described sections [12.1.3](#) and [12.3](#). Safety variables collected during the exposure period will also be reported by product exposure.

Adverse event data will serve as the primary assessment of safety. Other safety variables monitored in this study include: respiratory symptoms (cough assessment VAS and Likert scales); vital signs (systolic and diastolic blood pressure, pulse rate, respiratory rate); spirometry; ECG data; clinical chemistry, hematology, concomitant medications, and urine analysis safety panel; physical examination.

The number and percentage of subjects with AEs and SAEs will be tabulated by system organ class and preferred term. Summaries will also be presented for AEs leading to withdrawal, AEs leading to death, AEs by relatedness to product exposure, AEs by severity, and laboratory AEs. Tabulations will be performed for both the number of subjects experiencing an event and the number of events.

The number and percentage of subjects with clinical findings will be tabulated by sequence for laboratory parameters. Shift tables showing change from Baseline of clinical findings will be provided for ECGs, physical examinations, and laboratory parameters (both shifts in normal ranges and toxicity grades). Descriptive statistics will be summarized by visit and change from Baseline for laboratory parameters, ECG, respiratory symptoms, and vital signs.

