PP	Per protocol
PT	Preferred Term
PX	Paraxanthine
QC	Quality control
QSU-brief	Questionnaire of Smoking Urges
QTcB	QT Interval Corrected using Bazett's Formula

QTcF	QT Interval Corrected using Fridericia's Formula
RRP	Reduced risk products
SA	Smoking Abstinence
SAP	Statistical Analysis Plan
S-BMA	S-benzylmercapturic acid
SD	Standard deviation
SDTM	Standard Data Tabulation Modul
SES	Socio-Economic Status
sICAM-1	Soluble inter-cellular adhesion molecule-1
SOC	System Organ Class
SOP	Standard Operating Procedure
S-PMA	S-phenylmercapturic acid
T	Time point
TAC	Total anti-oxidant capacity
TC	Total cholesterol
TFL	Tables, Figures, and Listings
TG	Triglycerides
Total 1-OHP	Total 1-hydroxypyrene
Total 3-OH-B[a]P	Total 3-hydroxybenzo(a)pyrene
ULOQ	Upper Limit of Quantification
VAS	Visual Analogue Scale
WBC	White blood cell (count)
WHO	World Health Organisation
YG1024+S9	Ames Mutagenicity Test

The following special terms are used in this SAP:

Admission period	Day -3 until start of baseline period.
Baseline period	06:30 AM at Day -2 until 06:29 AM of Day 1.
Carbon Heated Tobacco Product 1.2 (CHTP 1.2)	CHTP 1.2 is a non-menthol tobacco stick which is comparable in shape and form, and is used in a similar manner to a combustible cigarette except that the tobacco contained in the CHTP 1.2 is heated by a Carbon Heat Tip and not burned like in a combustible cigarette.
Combustible cigarette (CC)	The term 'combustible cigarette' refers to commercially available cigarettes (manufactured) and excludes cigars, pipes, bidis, and other nicotine-containing products.
Completer	A subject is considered to have completed Confinement, period 2, 3 and 4 if he/she did not discontinue before Day 6, Day 30 Visit, Day 60 Visit, and Day 90 Visit respectively, and Completed safety follow-up.
Day of Discharge in the Confinement setting	Day 6 or early discontinuation in confinement.
Day of Discharge in the Ambulatory setting	Second day of Day 90 Visit.
Enrolment	On Day -3 for eligible subjects after all applicable inclusion and exclusion criteria have been satisfactorily met.
Enrolled	A subject is considered as being enrolled once he/she is declared for being enrolled in the IxRS.
Exposure period	In the confinement setting: 06:30 AM of Day 1 until the time of discharge on Day 6. In the Ambulatory Setting: from Discharge on Day 6 until Discharge at Day 90 Visit.

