12.5.4.3 Clinical Laboratory Evaluation

Table 18 below lists the hematology, clinical chemistry and urine analysis parameters to be assessed in this study.

Table 18: List of Laboratory Safety Parameters		
Hematology	Clinical Chemistry	Urine Analysis
Hematocrit	Albumin	pH
Hemoglobin	Total protein	Bilirubin
Mean corpuscular hemoglobin	Alkaline phosphatase	Glucose
Mean corpuscular hemoglobin concentration	Alanine aminotransferase	Nitrite
Mean corpuscular volume	Aspartate aminotransferase	Red blood cell traces
Platelet count	Blood urea nitrogen	Protein
Red blood cell count	Creatinine	Specific gravity
White blood cell (WBC) count	Gamma-glutamyl transferase	Urine sediment
Differential WBC count:	Fasting glucose	
• Neutrophils	Lactate dehydrogenase	
• Basophils	Potassium	
• Eosinophils	Sodium	
• Lymphocytes	Total bilirubin	
• Monocytes	Direct bilirubin	
	Total cholesterol	
	Triglycerides	

Any clinical safety laboratory test result that is outside of the normal reference range will be reviewed by the PI and assessed for clinical relevance. If the PI considers the abnormal result to be of clinical relevance, then it must be recorded as a concomitant disease at Screening, or if not present at Screening, as an AE during the study. If the condition worsens from screening to after product-use it will be recorded as an AE.

The grading scheme used in the Common Terminology Criteria for Adverse Events and Common Toxicity Criteria [CTCAE] version 4.03) will be used by the PI to assess abnormal laboratory AEs. These CTCAE grades will be derived programmatically in the creation of the datasets.

Laboratory data will be summarized (Table 15.2.6.11-13) and listed by arm, subject and parameter, at Screening and Day -1 for the Pre-Randomization period and at Day 6, Day

30 Visit, Day 60 Visit and Day 90 Visit for the Randomized period, together with numerical changes from baseline (Listing 15.3.6.2 - Listing 15.3.6.4). The number and percentage of subjects with normal results, high/low results, abnormal clinical result (as defined by PI comment) and with shift in normality and shift in toxicity grading from baseline will be tabulated for laboratory parameters.

[figure not shown]

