12.5.4.5.5 Electrocardiogram

The ECG data will be obtained directly from the 12-lead ECG traces, i.e. not centrally read. These data include the PR, QT, and QT interval corrected using Fridericia's formula (QTcF) intervals; QRS duration; and heart rate; and shift in normality evaluation (normal, abnormal, clinically relevant, together with any PMI comments to the abnormality).

ECG data values and normality evaluations will be listed by arm and study day (Screening, Day -1, Day 6 and Day 90 Visit) together with changes from baseline and shift in normality. ECG data from subjects which had significant clinical findings will be flagged in listings (Listing 15.3.6.10).

Descriptive statistics will be presented for ECG data at baseline, Day 6 and Day 90 Visit by arm. ECG data will be summarized together with changes from baseline, and the number and percentage of subjects with normal/abnormal/abnormal clinically significant results (Table 15.2.6.20 and Table 15.2.6.21).

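### Ambulatory early-termination results have no assigned summary timepoint, and unscheduled values are excluded from summaries with no exception for safety shift tables

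*SAP*

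**What the plan says.** Protocol 9.5 introduces its Table 19 with "Early termination procedures will be as follows, unless the subject refuses to do so". The table lists laboratory tests, safety urine analysis, pre- and post-bronchodilator spirometry, vital signs, ECG and physical examination. Protocol 8.6 applies these procedures to subjects discontinued for an adverse event.

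The SAP ties its safety summaries to named visits. For ECG: "Descriptive statistics will be presented for ECG data at baseline, Day 6 and Day 90 Visit by arm". Spirometry (SAP 12.5.2.4) uses the same three points. Laboratory data (SAP 12.5.4.3) are summarised at Screening, Day -1, Day 6 and then Day "30 Visit, Day 60 Visit and Day 90 Visit for the Randomized period".

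The SAP's terms section defines the day of discharge in confinement as "Day 6 or early discontinuation in confinement". The matching ambulatory entry names only the second day of the Day 90 Visit.

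For values outside the schedule, SAP 12.1.6 says "Unscheduled assessments will be excluded from the summary statistics" and "Unscheduled assessments will be labelled as unscheduled in the listings and mapped to the study day using the date of the study day until midnight". SAP 12.1 adds "All unscheduled assessments will be included in the listings".

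Protocol 12.5.4 promises shift tables: "Shift tables showing change from Baseline of clinical findings will be provided for ECGs, physical examinations, and laboratory parameters", with laboratory shifts in both normal range and toxicity grade.

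**The concern.** Subjects who leave because of an event or an abnormal finding tend to have informative exit results. If those results have no row, and repeat values between visits are left out, the summary and shift tables for the 85-day ambulatory period mainly describe subjects who stayed to the next visit. ECG and spirometry are the most exposed, because neither has a scheduled measurement between Day 6 and the Day 90 Visit. For a subject who leaves in that interval, the exit test is the only planned one after Day 6.

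**Working it through.** No figure in the plan needs reproducing, so the check sets the passages side by side.

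**1. What is measured at exit, and where it could be summarised**

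| Assessment | In Protocol Table 19 | SAP summary points after Day 6 | Timepoint basis of shift |
|---|---|---|---|
| ECG | yes | Day 90 (12.5.4.5.5) | not stated (Table 15.2.6.21) |
| Spirometry | yes | Day 90 (12.5.2.4) | not stated (Table 15.2.4.20.1) |
| Laboratory, urine | yes | Days 30, 60, 90 (12.5.4.3) | not stated |
| Physical examination | yes | Days 30, 60, 90 (12.5.4.5.4) | per timepoint |
| Vital signs | yes | Days 30, 60, 90 (12.5.4.5.2) | no shift planned |

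The table list in SAP 13.3.1 has no early-termination, last-value or worst-value table for any of these. SAP Table 14 (assessment windows) has no early-termination entry. No rule turns an exit near Day 30 or Day 60 into that visit's result.

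**2. How an ambulatory exit result could be handled**

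- If it is treated as unscheduled, SAP 12.1.6 removes it from the summaries.
- If it is treated as planned, none of the named timepoints is defined to receive it.
- It could also be misfiled. A footnote to the schedule of events, in both documents, says that discontinuing subjects have the Day 6 discharge examinations. A programmer could therefore label a Day 50 exit as Day 6.

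**3. Length of the uncovered interval**

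Protocol 9.3 allows ±5 days around Visit 4, so its first day can fall as early as 90 − 5 = Day 85.

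- Strict count: Days 7 to 84, 84 − 7 + 1 = 78 days.
- Nominal count: Days 7 to 89, 89 − 7 + 1 = 83 days.

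This is a calendar span, not a frequency.

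**4. Unscheduled values and shift tables**

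SAP 12.1.3 places frequency counts and percentages for categorical data under descriptive statistics. Shift counts are therefore arguably caught by the 12.1.6 exclusion, and no text exempts them. An abnormal value seen only at a repeat test between visits would then not count.

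**5. What other routes capture**

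Protocol 8.4 covers laboratory results after Screening. Clinically significant and Grade 2 or higher values are reported as adverse events or linked to an existing event or concomitant disease, and worsening in grade is reported as an adverse event. This does not depend on visit type. It does not cover a first Grade 1 value or a normal-range shift judged not clinically significant, and a value linked to a concomitant disease need not create a new event. For ECG, Protocol 7.3.10.2 asks for a diagnosis when a trace is clinically significant but gives no matching reporting rule, although the general definition in Protocol 8.1.1 could apply.

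**The case against.** The strongest reply is that SAP 12.1.6 concerns unplanned data, while early-termination tests are planned by the protocol. Nothing in the SAP calls them unscheduled, so their exclusion would rest on silence. The named-visit wording for ECG and laboratory tests is attached to descriptive statistics; their shift tables state no timepoint. Table layouts sit in a separate shells document (SAP section 3) that is not available here.

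Adverse events are the primary safety assessment (Protocol 12.5.4). They are tabulated by study period, with a table for events leading to study discontinuation (15.2.6.6). Listings carry unscheduled values, laboratory grades and shifts, and flags for significant ECG and spirometry findings. With about 120 subjects, such listings can be read. A worst-value shift also gives subjects with repeat tests more chances to shift.

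Most of this stands and limits the point. A reader might infer that exit results appear in no table, that the plan expressly bars them, or that all shift tables are restricted to nominal visits. The documents support none of these. Serious laboratory findings have a route to the adverse event tables, the exclusion of exit results is not stated, and the laboratory, ECG and spirometry shift bases are left open. Nor does the point reach every subject who stops a product: those who quit or use other products during the ambulatory period remain in the study, and those who leave may refuse the exit tests.

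The silence itself is not answered. Neither way of classifying an exit result gives it a summary row.

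**Conclusion.** The point holds as a gap in the analysis rules that should be closed before database lock. Unscheduled values are excluded from summaries with no stated exception for safety shifts. Ambulatory exit results for ECG, laboratory tests, spirometry, vital signs and physical examination have no assured place in the by-visit summaries or, where shifts are planned, in the shift tables. The interval concerned is 78 days on the strict window, or 83 on the nominal one.

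The number of subjects affected cannot be given, because the documents state no expected dropout rate. The conclusion assumes that the subject leaves the study and accepts the exit tests, and that the unseen shells do not already supply the missing rows. It does not mean that safety signals are lost: values stay in listings and the adverse event route operates for laboratory results. It means that the shift tables may understate how many subjects ever moved to an abnormal result.

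**What to change.** 1. In SAP 12.1.6, limit the exclusion of unscheduled values to by-visit descriptive statistics.
2. State that an ambulatory early-termination assessment is reported under its own 'Early termination' row, not under Day 6. Add that row to Tables 15.2.6.11-13, 15.2.6.17, 15.2.6.19-21, 15.2.4.19.1 and 15.2.4.20.1.
3. Add a worst post-baseline shift per subject using all post-baseline values, including unscheduled and early-termination ones. Use normality and CTCAE grade for laboratory tests, and the normal, abnormal or clinically significant category for ECG, spirometry and physical examination. Add none for vital signs, which have no categories.
4. Footnote that subjects with repeat tests have more chances to shift.

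The method is already in the SAP: the cough tables over the study take the most severe response (12.5.2.5), and adverse event incidence takes the worst occurrence (12.5.4.2.1).

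The cost is SAP wording and some table rows and programming; the data are already collected. Worst-value rates will be somewhat higher than by-visit rates. Under SAP 12.1.5.1 an early-termination row with fewer than four subjects would show only the count, minimum and maximum, so the worst post-baseline shift is the more useful of the two additions.
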